### **6. CHANGES IN THE PLANNED ANALYSES**

1. Day 0 is the earliest day that study drug is initiated but will be designated as Day 1 based on implementation standards for the analysis.
2. Central imaging review was not completed; therefore, results from this will not be presented.
3. The following analyses will not be completed:
  - a. Durable radiographic response (DRR)
  - b. Duration of disease control (DDC)
  - c. Progression-free survival (PFS)
  - d. Analysis of Per-Protocol population
  - e. Analyses based on participant strata (prior anti-VEGF agents, prior chemotherapy use)
  - f. Analyses on the efficacy set and PP set for the following subgroups: baseline NANO score, KPS, prior bevacizumab and chemotherapy or other treatment use/failure, extent of surgery at diagnosis, MGMT promoter methylation status and/or other tumor genetic factors at diagnosis and baseline, lesion cross-sectional area at baseline, number of prior progressions, age, gender.

- g. Landmark survival at month 24
- h. Exploratory analyses including analysis of efficacy based on modified iRANO criteria in Section 8.4.6.1, Table 3 of the protocol, identification of biomarkers of anti-tumor response to lerapolturev following by pembrolizumab or assessment of patient reported outcomes
- 4. The entire anticipated sample size of patients was not enrolled.

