#### 2.1.1 Primary Efficacy Endpoints

- ORR: Proportion of patients with confirmed CR or PR.
- DOR: KM curves showing median DOR for all patients that have confirmed CR or PR.
- DRR: Proportion of patients with confirmed response (CR or PR) that lasts for  $\geq 6$  months.

Objective response (CR or PR), stable disease and confirmed progression will be determined via criteria noted in **Table 3**.

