#### **8.4.6.3 Progression Free Survival**

If calculable, PFS will be based on the time of first PVSRIPO infusion to death or unequivocal confirmed progression, based on the definition of progression noted in **Table 3**.

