## 5.7. EFFICACY

### 5.7.1. Primary Efficacy Endpoints

The primary efficacy endpoints are ORR and DOR.

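### The SAP drops durable radiographic response, one of the protocol's three primary efficacy endpoints, without a reason, and reports no 6-month durability figure in its place

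*SAP*

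**What the plan says.** Protocol Section 2.1.1 lists ORR, DOR and a third primary efficacy endpoint, "DRR: Proportion of patients with confirmed response (CR or PR) that lasts for" 6 months or more. The synopsis and Table 2 list the same three. SAP Section 5.7.1 has two: "The primary efficacy endpoints are ORR and DOR". SAP Section 2 agrees with it.

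The removal is declared in SAP Section 6. Under the lead-in "The following analyses will not be completed", item 3a is "Durable radiographic response (DRR" and item 3c is "Progression-free survival (PFS". No entry in that list carries a reason. Two other items in the section might be taken for one: "Central imaging review was not completed; therefore, results from this will not be presented" (item 2) and "The entire anticipated sample size of patients was not enrolled" (item 4). Both are numbered separately, and neither is linked to DRR or PFS.

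For DOR, SAP Section 5.7.1.2 plans the numbers progressed or dead and censored, the median and quartiles with 95% intervals, and a Kaplan-Meier curve. It plans no rate at 6 months.

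PFS had a different standing. Protocol Table 2 makes it secondary, and Section 8.4.6.3 makes it conditional: "If calculable, PFS will be based on the time of first PVSRIPO infusion to death or unequivocal confirmed progression", with progression as defined in Table 3.

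**The concern.** A primary endpoint has been taken out of an open-label trial by a SAP that already knew recruitment had fallen short. Without a stated reason, a reader of the report cannot tell a practical decision from a selective one.

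The content matters too. DRR was the only primary endpoint that put durability over everyone treated. ORR counts a response of a few weeks the same as one of a year, since the SAP's CR and PR definitions ask for 4 weeks. DOR is conditional on having responded, so it says how long responses lasted but not what share of treated patients had a lasting one. With few responders, its median may also not be estimable.

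**Working it through.** **The plan's own figure.** The only design calculation is for ORR: more than 75% power with 30 patients, 11% against 31%, two-sided 0.05. An exact binomial check reproduces it. The smallest count with an upper tail of at most 0.025 under 11% is 8 of 30 (tail 0.0135; 7 of 30 gives 0.041). Under 31%, the probability of 8 or more responders is 75.7%. No design figure exists for DRR, so restoring it changes neither sample size nor power.

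**Can DRR be derived from what the SAP keeps?** SAP Section 3.2.6 runs DOR from response to confirmed PD or death, with censoring. Each responder therefore falls into one of three groups:
- followed to 6 months without an event (durable);
- event before 6 months (not durable);
- censored before 6 months (unknown).

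DRR is the first group divided by N of the efficacy set. No new data are needed.

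**How many patients does DOR describe?** 0.11 × 30 = 3.3 and 0.31 × 30 = 9.3, so about 3 to 9 responders, leaving about 21 to 27 of 30 outside DOR. The actual N is not stated. It is below plan, so these counts would be smaller.

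**What would each summary show?** Assume 6 responders of 30 (ORR 20%) and three possible courses:

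| Assumed course of the 6 responders | Durable n/N | Censored before 6 months | KM DOR rate at 6 months | Median DOR |
|---|---|---|---|---|
| A: 4 events before month 6, 2 followed beyond | 2/30 = 6.7% | 0 | 2/6 = 33% | below 6 months |
| B: 4 censored before month 6, 2 followed beyond | 2/30 = 6.7% | 4 | 100% | not reached by month 6 |
| C: 2 events before month 6, 4 followed beyond | 4/30 = 13.3% | 0 | 4/6 = 67% | not reached by month 6 |

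In A the planned median already reveals short responses. B gives the same n/N as A only because follow-up ended: if all 4 censored responses had lasted, the proportion would be 6/30 = 20%. In C the median gives no 6-month figure. A and B can be told apart only if n/N, the number censored early and the Kaplan-Meier rate stand together.

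**Is early censoring likely?** Maximum follow-up is 24 months, so a response must begin by month 24 − 6 = 18 to be seen lasting 6 months. Protocol Section 8.4.6.1 gives a Phase 1 median time to response of 15.4 months (range 5.7 to 29.7). If timing is similar here, some responses would begin too late to qualify.

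**Precision.** Clopper-Pearson 95% intervals for an assumed 3 durable responses: 3/30 = 10% (2.1% to 26.5%); 3/20 = 15% (3.2% to 37.9%); 3/15 = 20% (4.3% to 48.1%). For 2/30 the interval is 0.8% to 22.1%.

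**The case against.** The best defence is that the change is declared, that Protocol Section 8 lets the SAP prevail, and that the SAP is descriptive, with no hypothesis test, so no error rate is at stake. The DOR output is also fuller than a bare median, and with few responders the listings let a reader trace each response. All of this is true. It limits the harm, but it does not supply a reason or a tabulated figure over all treated patients.

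A second defence is that DRR is biased downward if responders censored before 6 months count as failures. This also stands, and it could have been a sound reason for dropping DRR, but the SAP does not give it. The same censoring affects DOR, which was kept. It is a reason to show the censored number and the Kaplan-Meier rate beside DRR.

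Three stronger readings are tempting and are not supported:
- *PFS must be restored as well.* PFS was secondary and conditional on being calculable. DOR and OS dates do not yield it: DOR covers responders only and OS carries no progression date, so confirmed-PD dates in non-responders are needed. Protocol PFS also rests on Table 3, whose analysis the SAP drops. PFS by iRANO was exploratory (Protocol Section 2.3), and the protocol's opening notice calls such standard criteria not optimal for judging progression here.
- *Short responses would go unreported.* Course A shows that the planned median can reveal them.
- *DRR would settle bevacizumab pseudoresponse.* The SAP's response criteria contain no off-bevacizumab condition, so a 6-month response on continued bevacizumab would count as durable.

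**Conclusion.** The point holds for DRR. A protocol primary endpoint was removed without a reason, after enrolment had fallen short, although it can be counted from data that the SAP still derives, and nothing tabulated replaces it. What is lost is one proportion over the efficacy set and one Kaplan-Meier rate. ORR and DOR themselves are unaffected. The responder numbers assume ORR between 11% and 31% and N = 30, and the worked counts are illustrations.

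A reader might infer that DRR was dropped because of the results. The documents do not show that: the SAP reveals knowledge of enrolment, not of response durations. For PFS, the most that can be asked is a statement of whether it was calculable.

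**What to change.** Delete item 3a from SAP Section 6 and return DRR to the endpoint lists in SAP Sections 2 and 5.7.1. In Table 14.2.1.1 report:
- DRR as n/N of the efficacy set with a Clopper-Pearson 95% CI, on the same response criteria as ORR and DOR;
- the number of responders censored before 6 months, shown separately;
- the Kaplan-Meier DOR rate at 6 months, so that censoring is not read as failure.

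For item 3c, add one sentence saying whether PFS was calculable and, if not, why. Restoration is not required, since it would need progression dates in non-responders, a choice between Table 3 and iRANO progression, and censoring rules that the SAP does not now contain.

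The cost is a few table rows from data already derived. The downsides are wide intervals and a conservative DRR if late responders are censored.

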**7. REVISION HISTORY**

Date	Revision	Rationale
23 June 2022	NA	Original Document

**8. REFERENCES**

## 9. PROGRAMMING CONVENTIONS

- Page orientation, margins, and fonts: Summary tables, listings, and figures will appear in landscape orientation. There should be a minimum of a 1.0" boundary on the left and right edges. The top and bottom margins are 1.0" for tables and listings but may vary for figures. Output should be printed in Courier New with a point size of 8. Titles may be printed using a larger font (e.g., Arial point size 10).
- Identification of analysis population: Every summary table and figure should clearly specify the analysis population being summarized. Listings will be prepared for all participants.
- Group headers: In the summary tables, the group headers will identify the summary group and the sample size for the indicated analysis population. Of note, the header's sample size does not necessarily equal the number of participants summarized within any given summary module; some participants in the analysis population may have missing values and thus may not be summarized.
- Suppression of percentages corresponding to null categories: When count data are presented as category frequencies and corresponding percentages, the percent should be suppressed when the count is zero to draw attention to the non-zero counts.
- Presentation of sample sizes: Summary modules should indicate, in one way or another, the number of participants contributing to the summary statistics presented in any given summary module. As mentioned above, this may be less than the number of participants in the analysis population due to missing data.
  - In the quantitative modules describing continuous variables (and thus presenting sample size, means, and standard deviations), the sample size should be the number of non-missing observations. The number of missing observations, if any, will be noted.
  - For categorical variables that are presented in frequency tables, the module should present the total count in addition to the count in each category. Percentages should be calculated using this total as the denominator, and the percentage corresponding to the sum itself (that is, 100%) should be presented to indicate clearly to a reviewer the method of calculation. The number of missing observations, if any, will be noted.
- Sorting: Listings will be sorted participant number and date, if applicable. If a listing is sorted in a different manner, a footnote will indicate as such.
- General formatting rules: Rounding for all variables will occur only as the last step, immediately prior to presentation in listings, tables, and figures. No intermediate rounding will be performed on derived variables. The standard rounding practice of rounding numbers ending in 0-4 down and numbers ending in 5-9 up will be employed.
- Numerical Values: The presentation of numerical values will adhere to the following guidelines:
  - Raw measurements will be reported to the number of significant digits as captured electronically or on the CRFs.
  - Standard deviations will be reported to one decimal place beyond the number of decimal places the original parameter is presented.

- Means will be reported to the same number of significant digits as the parameter.
- Calculated percentages will be reported with no decimals.
- Dates will be formatted as DDMMYY YYYY. Partial dates will be presented on data listings as recorded on CRFs.
- Time will be presented according to the 24-hour clock (HH:MM).

## 10. PROPOSED TABLES, LISTINGS, AND FIGURES

### Summary Tables

#### Accountability and Baseline Characteristics

- 14.1.1.1 Participant Disposition, Screening Set
- 14.1.2.1 Demographics and Baseline Characteristics, Safety Set
- 14.1.3.1 Disease Characteristics, Safety Set
- 14.1.3.2 Summary of Prior Anti-Cancer Therapy, Safety Set
- 14.1.3.3 Summary of Tissue Biomarkers, Safety Set
- 14.1.4.1 Concomitant Medications, Safety Set
- 14.1.4.2 Bevacizumab Administration, Safety Set
- 14.1.4.3 Dexamethasone Use, Safety Set
- 14.1.5.1 Summary of Study Drug Exposure, Safety Set

#### Efficacy

- 14.2.1.1 Summary of Best Overall Tumor Response and Duration of Response by iRANO Criteria, Efficacy Set
- 14.2.2.1 Summary of Overall Survival, Efficacy Set

#### Safety

- 14.3.1.1 Overall Summary of Treatment-Emergent Adverse Events, Safety Set
- 14.3.1.2 Treatment-Emergent Adverse Events by System Organ Class, Preferred Term, and Greatest Severity, Safety Set
- 14.3.1.3 Treatment-Emergent Adverse Events by Preferred Term in Descending Frequency, Safety Set
- 14.3.1.4 Treatment-Emergent Adverse Events Related to Study Drug or Catheter by System Organ Class, Preferred Term, and Greatest Severity, Safety Set
- 14.3.1.5 Treatment-Emergent Adverse Events Related to Study Drug or Catheter by Preferred Term in Descending Frequency, Safety Set
- 14.3.1.6 Treatment-Emergent Serious Adverse Events by System Organ Class, Preferred Term and Greatest Severity, Safety Set
- 14.3.1.7 Treatment-Emergent Serious Adverse Events Related to Study Drug or Catheter by System Organ Class, Preferred Term, and Greatest Severity, Safety Set
- 14.3.1.8 Treatment-Emergent Dose Limiting Toxicities by System Organ Class, Preferred Term and Greatest Severity, Safety Set
- 14.3.1.9 Treatment-Emergent Adverse Events of Special Interest for Lerapoltrev by System Organ Class, Preferred Term, and Greatest Severity, Safety Set
- 14.3.1.10 Treatment-Emergent irAEs for Pembrolizumab by System Organ Class, Preferred Term, and Greatest Severity, Safety Set
- 14.3.1.11 Treatment-Emergent Adverse Events Leading to Discontinuation of Study Treatment by System Organ Class, Preferred Term, and Greatest Severity, Safety Set
- 14.3.4.1 Summary of Grade Shifts in Laboratory Abnormalities – Hematology, Safety Set
- 14.3.4.2 Summary of Grade Shifts in Laboratory Abnormalities – Chemistry, Pancreatic and Thyroid, Safety Set

- 14.3.4.3 Number of Participants with at Least One ALT, AST, or Total Bilirubin Above Upper Limit of the Normal Range Post-Baseline, Safety Set
- 14.3.4.4 Summary of Vital Signs by Visit, Safety Set
- 14.3.4.5 Summary of Karnofsky Performance Status by Visit, Safety Set
- 14.3.4.6 Summary of Neurologic Assessment in Neuro-Oncology Score by Visit, Safety Set

### **Summary Figures**

#### **Efficacy**

- 14.2.1.2 Overall Survival – Kaplan Meier Curve, Safety Set
- 14.2.2.2 Duration of Response – Kaplan Meier Curve, Safety Set

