#### Overall Survival (OS)

OS is defined as time from first lerapoltrev infusion to death from any cause, or last follow-up if participant is alive.

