**4.1.        EFFICACY ANALYSIS SET**

The primary efficacy analysis set includes all participants who received at least one dose of lerapoltrev and  $\geq 1$  dose of pembrolizumab. This will be the primary population used for the efficacy analyses. Analyses using the efficacy set will be conducted based on the treatment received.

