**4.2.        SAFETY ANALYSIS SET**

The SAF includes all enrolled participants who had an infusion catheter placed. This will be the primary population used for the safety analyses. Participants in the SAF set will be analyzed based on the treatment received.

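### SAP 10 puts the OS and DOR Kaplan-Meier figures on the Safety Set, while their tables, SAP 4.1 and the estimand use the Efficacy Set

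*SAP*

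**What the plan says.** The list of proposed outputs in SAP 10 names two efficacy figures, each with a title ending "Kaplan Meier Curve, Safety Set":

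- "14.2.1.2 Overall Survival – Kaplan Meier Curve, Safety Set"
- "14.2.2.2 Duration of Response – Kaplan Meier Curve, Safety Set"

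The tables for the same two endpoints are on a different population:

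- Table 14.2.2.1: "Summary of Overall Survival, Efficacy Set"
- "14.2.1.1 Summary of Best Overall Tumor Response and Duration of Response by iRANO Criteria, Efficacy Set"

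SAP 4.1 defines the Efficacy Set as participants with at least one dose of lerapolturev (PVSRIPO in the protocol) and at least one of pembrolizumab, and adds: "This will be the primary population used for the efficacy analyses". SAP 4.2 is wider: "The SAF includes all enrolled participants who had an infusion catheter placed".

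The primary estimand in SAP 5.7.1.1 rests on the Efficacy Set. SAP 5.7.1.2 calls for the DOR curve within an analysis of participants who received both agents. For survival, SAP 3.2.6 fixes the start of the clock: "OS is defined as time from first lerapoltrev infusion to death from any cause". SAP 6, which lists departures from the planned analyses, says nothing about a different population for the curves.

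**The concern.** A Kaplan-Meier curve and the table beside it are normally read as two views of one estimate. Here the titles assign them to two populations, and the wider one differs in a way that matters. Protocol 3.2 withholds pembrolizumab from patients whose edema-related events have not resolved by week 4, who need dexamethasone above the stated limit before the first dose, or who are undosed by week 4 for any reason. Those patients are replaced. Several of the reasons are clinical, so the patients added to the curve are unlikely to be a random sample of those treated.

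Protocol 4.5 keeps these patients out of the combination datasets, and protocol 8.4.6 has them analysed apart. The SAP offers no counterweight: section 5 presents every table and figure for the overall population, so no PVSRIPO-only curve is planned. Protocol 8 also lets the SAP govern where the two documents differ. At stake is whether the survival curve describes the combination, which is the treatment of interest in the estimand.

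**Working it through.** **Setting the texts side by side**

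| Endpoint | Table population | Figure population | Population in the SAP body |
|---|---|---|---|
| DOR (primary) | Efficacy Set (14.2.1.1) | Safety Set (14.2.2.2) | Efficacy Set (4.1, 5.7.1.1, 5.7.1.2) |
| OS (secondary) | Efficacy Set (14.2.2.1) | Safety Set (14.2.1.2) | Efficacy Set (4.1) |

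**Who could be in the Safety Set but not the Efficacy Set**

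1. *Infused, no pembrolizumab.* They have a catheter and an infusion date, so they have a valid OS time and would enter the OS curve. They could enter the DOR curve only as responders, because SAP 3.2.6 starts DOR at objective response.
2. *Catheter placed, never infused.* Protocol 5.2.1 allows the catheter to be placed while the diagnosis is pending. Such a patient has no OS start date, and the SAP gives no substitute. A footnote to the SAP schedule of assessments calls a patient who is not infused a screen failure, and SAP 4.2 requires enrolment, so Safety Set membership is itself unclear.

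The OS curve and table therefore differ if at least one patient of type 1 exists. The DOR curve and table differ only if at least one of them responds.

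**Size: no count is given, so illustration only**

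The documents do not state how many patients were infused without pembrolizumab. Assumptions: 30 Efficacy Set patients (the planned number) with exponential survival and median 10 months, the upper end of the 6 to 10 months that protocol 1 gives for this disease; and k infused-only patients with median m of 3 or 6 months. The pooled curve is

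S(t) = [30 × 2^(−t/10) + k × 2^(−t/m)] / (30 + k),

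and its median solves S(t) = 0.5:

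| k | m = 3 | m = 6 | Table median |
|---|---|---|---|
| 0 | 10.0 | 10.0 | 10.0 |
| 1 | 9.63 | 9.83 | 10.0 |
| 3 | 8.96 | 9.53 | 10.0 |
| 5 | 8.38 | 9.26 | 10.0 |

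Landmark rates for k = 3:

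- 6 months: table 2^(−0.6) = 66.0%. Curve (30 × 0.6598 + 3 × 0.25)/33 = 62.3% for m = 3; (30 × 0.6598 + 3 × 0.50)/33 = 64.5% for m = 6.
- 12 months: table 2^(−1.2) = 43.5%. Curve (30 × 0.4353 + 3 × 0.0625)/33 = 40.1% for m = 3; (30 × 0.4353 + 3 × 0.25)/33 = 41.8% for m = 6.

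SAP 6 records that the planned sample was not fully enrolled, so each extra patient would weigh more than in this example.

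For DOR, suppose each infused-only patient responds with probability 0.11, the Phase 1 rate for PVSRIPO alone in SAP 3.1. The chance that none responds, and the DOR curve is unchanged, is 0.89^k: 0.89 for k = 1, 0.70 for k = 3 and 0.56 for k = 5.

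**Design figure**

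The one stated design figure, power above 75% for 11% against 31% with 30 patients, does not depend on this point. It reproduces: an exact binomial rule of at least 8 responses in 30 has one-sided alpha 0.0135 and power 75.7%.

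**The case against.** The best defence is that the analysis is already settled in the body of the SAP. Sections 4.1, 5.7.1.1 and 5.7.1.2 are clear, and the conflict sits only in a list of proposed outputs. The figure numbers in the same two lines are crossed: the OS figure carries a number from the response and DOR series, and the DOR figure one from the OS series. That points to one clerical slip. SAP 9 also requires each figure to name its population, so a reader would see the difference. This all stands as an account of how the titles probably arose. It does not make them harmless, because a programmer would follow the listed title.

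A second point also stands in part. Protocol 8.4.6 defines a full efficacy set of everyone infused, and protocol 8 and 8.2 say all treated patients will be summarised in all analyses. An all-treated survival curve is thus not foreign to the protocol. But the SAP does not declare these figures as supportive analyses, and its Safety Set is defined by catheter placement, not infusion.

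A reader might infer that never-infused patients will appear in the curves. The documents do not support that. OS runs from infusion and DOR from response, so under the SAP's own definitions such a patient has nothing to plot. The schedule footnote calls them screen failures, and protocol 4.5 treats those who withdraw before infusion as evaluable only in the screening set. What remains is an unstated rule, not a known inclusion.

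**Conclusion.** The titles contradict the rest of the SAP, and nothing in SAP 6 explains it. The firm consequence concerns OS: as written, its curve would mix any infused patients without pembrolizumab into the combination group, and so may not match the tabulated median and landmark rates. For DOR the effect is conditional on a response in such a patient, and there may be none.

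Two further inferences go too far. One is that curve and table are bound to disagree; the two sets could turn out identical, and the documents give no count either way. The other is that the reported medians, confidence intervals or 6- and 12-month rates are wrong; these belong to the Efficacy Set tables and are untouched. The shift to a median of 8.4 to 9.8 months for one to five extra patients, against 10.0, rests wholly on the assumed survival times, the assumed counts and a base of 30 that was not reached. It shows that a few patients could make a visible difference, not that they did.

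**What to change.** Retitle figures 14.2.1.2 and 14.2.2.2 to the Efficacy Set, and correct the crossed numbers at the same time. If a curve for all treated patients is wanted, list it as a separate, clearly labelled supportive figure on infused patients, with PVSRIPO-only patients shown apart. If any survival figure stays on the catheter-based Safety Set, the SAP must state how a never-infused patient is handled.

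The cost is two title edits and the matching population selection in the programs. No data collection, sample size, power, alpha or tabulated result changes.
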